# **Exclusion Criteria:**

- Allergic reactivity to hyaluronic acid
- Current knee infection, infection around injection site or any skin disease
- Pregnancy or lactation
- Participating in other clinical trial
- Any reason that may jeopardize the collection of data (patient likely to be lost-to-follow up)

# 5.4 Duration of Study Period and Follow-up

All patients will be followed during 26 weeks after the first injection with Suplasyn®. The study end date will be considered when the last patient has completed the observation period.

#### 5.5 Intended Intervention

- 2ml of Hyaluronic Acid Intra-articular Injection (Suplasyn®) on the affected knee at baseline (Day 1), one week (Week1) and two weeks (Week 2) after initiation of the viscosupplementation VS treatment.
- Paracetamol, NSAID or analgesics are allowed as a rescue medication if unbearable pain had not improved after at least 1 hour rest.
- Glucosamines and chondroitines or other slow-acting drugs for osteoarthritis (i.e. diacerhein or avocado/soybean unsaponifiables) are allowed if at a stable dosage for 3 months or more.
   Consumption of rescue or other medication is recorded in a patients data form.

### 5.6 Sample size calculation

As it is an observational study of descriptive nature, a minimum margin to obtain statistical significance has not been settled. An estimated sample of 300 patients that have could be recommended during the established period for inclusion of data is considered.

### 6 MAIN VARIABLES

#### 6.1 Main Variables for Evaluation

- Knee pain symptoms
- Physical function
- Quality of Life (QoL)
- Safety (Adverse Events)
- Compliance with treatment

#### 6.2 Measures

The quality-of-life questionnaires that are completed by the patient with no input from the healthcare personnel may be more objective, because they more faithfully reflect the experience of the patient. In

knee osteoarthritis treatment, the self-assessed Oxford Knee Score (OKS) and Visual Analog Scale (VAS) are widely used.

✓ Patients Outcome assessed with the Oxford Knee Score (OKS) (39): Describes any changes from baseline over a period of 6 months; the study subjects will complete personally the (OKS) questionnaire at baseline, 1 and 6 months following the viscosupplementation of the knee.

This is a "self-administered" questionnaire. It has 12 items on daily activities, which the patient must answer without help from healthcare personnel. Each item is scored from 1 (normal function) to 5 (extreme difficulty). The global score is the sum of the 12 item scores. Therefore, the best possible score is 12 and the worst possible score is 60. Partial scores have also been defined, for pain (questions 1, 4, 5, 8 and 9) (5–25 points), range of motion (questions 2, 3, 7 and 12) (4 – 20 points) and walking (questions 4, 6, 9, 10 and 11) (5–25 points).

The OKS is a disease-specific, purpose built, high performance instrument for evaluative research in knee osteoarthritis clinical trials. It assesses the outcome, as judged by the patient. This is of value in the large multicenter trials. (40-42) The OKS questionnaire may be compared with others that have been successfully applied to the treatment of osteoarthritis, but it has the advantage over assessments such as the Western Ontario and McMaster Universities Osteoarthritis Index (WOMAC) and the Arthritis Impact Measurement Scales (AIMS), in that it is intended specifically for use with knee surgery and knee OA treatment alone, and is simpler and quicker to process (37,38).

# ☑ Pain evaluated with the Visual Analog Scale (VAS)

The (VAS) will describe the change in the level of knee pain from baseline following viscosupplementation of the knee. (Time Frame: The study subjects will complete the (VAS) at baseline, 1 and 6 months following the viscosupplementation of the knee.)

**The (VAS)** responses are expressed on a 100 mm line, with 0 representing no pain and 100 mm representing the worst pain possible. (43,44) The patient places a mark across the line representing where their perceived pain lies, from no pain to severe pain; measured at rest (night) and during daily activities.

#### ☑ Safety assessment

Adverse events observed by the doctors or reported by the patients spontaneously or following a non-leading questions, will be collected on patient data form. Particular attention will be paid to local painful

reactions at the injection site, post-injection reactions (i.e. effusion, skin rush, swelling, warmth) and acute pseudoseptic arthritis (36).

☑ Compliance will considered based on the a posteriori analysis of the number of visits and number of doses applied for each patient. A discontinuation is defined as an interruption of recommended regimen of three weekly doses at any point of that period.

# 7 STATISTICAL ANALYSIS

All data will be analyzed with the statistical software SPSS-Windows.

# 7.1 Descriptive Statistics

All variables recorded will be descriptively analyzed. Categorical variables will be presented as frequencies and proportions. Quantitative factors (continuous/ordinals) will be also presented as central tendencies indexes (mean, median) and dispersion measures (standard deviation, minimum and maximum values).

# 7.2 Study Objectives

Primary outcome is to assess in real-life practice the effectiveness of viscosupplementation treatment using triple Suplasyn® 2ml injections (20 mg/2ml sodium hyaluronate, 500-1000kDa MW). The primary efficacy endpoint is the change from baseline in the Oxford knee score assessing the **function** of the OA knee at 4 and 26 weeks and the change from baseline in the patient-rated knee OA **pain** assessment (100 mm visual analogue scale/VAS) at 4 and 26 weeks.

Both scores obtained with the Oxford Knee Score and Pain VAS will be registered at 1 and 6 months following viscosupplementation of the knee.

Secondary objectives correspond to the evaluation of the **safety profile and adverse events** (AEs) of Suplasyn® 2ml injections, assessment of **concomitant consumption of permitted rescue medications** (analgesics, NSAIDs) throughout the study and the known the **characteristics of the beneficiary population** (intend-to-treat).

Continuous variables will be expressed as mean ± Standard Deviation (SD) while categorical binary variables will be presented as percentages.

Both primary and secondary objectives will be analyzed with tests for repeated measures to determinate the evolution of the variables throughout study visits. P values <0.05 will be considered as statistically significant.

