# 3.2 Secondary Objectives

- To evaluate the safety profile and adverse events (AEs) of Suplasyn® 2ml injections.
- To evaluate the concomitant consumption of permitted rescue medications (analgesics, NSAIDS) throughout the study.
- To evaluate characteristics of the beneficiary population (Intended to treat).

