# 9 PRACTICAL CONSIDERATIONS

# 9.1 Work plan

All researches will have to register to be assigned with a personal id and password for access to study online surveys. Once the researcher has signed the *researcher commitment form* and have received a confirmation of his/her registration can proceed to the inclusion of data.

Patients will be selected from those who accomplish inclusion criteria, based on the consecutive sampling technique. Researcher will proceed to explain patient about the study and ask for a signature on the *consent form* prior to the inclusion.

It is important to keep in mind that the recommendation with Suplasyn® for the viscosupplementation of the affected knee is not conditioned to the development of the study or the inclusion of a specific patient in this study.

Data will be recorded by the researcher in an online electronic Case Report Form (eCRF) to which will access with their id and password. The online platform will assign to each patient an automatic and unique code which will allow registering his/her clinical information throughout all study visits for the later generation of a database and an analysis of the final results. The eCRF does not contain any patients' personal information and the researcher is committed to keep the access information and the content of the eCRFs in complete anonymity, besides the obligation to accomplish with the principles and laws applicable in his/her local context, being fully responsible for the truthful of the provided data.

- On visit 1 (baseline) patient will receive the first intraarticular injection of 2ml of Hyaluronic
  Acid Suplasyn® in the affected knee following the product instructions leaflet and according to
  standard measures for these types of procedures. In this visit, patient will also have to complete
  the Patient eCRF which includes the OKS.
- On visit 2 (administration of the second HA injection, one week after first injection) and Visit 3 (administration of the third HA injection, one week after second injection) adverse events should be investigated. In case the researcher obtains as a response to the question

"How did you feel since your last visit" any adverse event since prior visit, the *Adverse Event* Form should be completed and sent to the study coordinator.

- Visit 4 (1 month after injection): Researcher will complete the eCRF corresponding to that
  visit by recording data on patient's consumption of any pharmacological treatment for pain

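### Section 7.2 assigns every objective to repeated-measures tests at P<0.05, a method that does not answer the adverse-event objective and has no hypothesis for once-recorded population characteristics

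*Protocol*

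**What the plan says.** The secondary objectives stand in Protocol section 3.2 and again in 7.2. The safety objective is "To evaluate the safety profile and adverse events (AEs) of Suplasyn® 2ml injections". The second is "To evaluate the concomitant consumption of permitted rescue medications (analgesics, NSAIDS) throughout the study". The third is to describe the characteristics of the treated population.

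Section 7.2 sets one inferential method for all of them: "Both primary and secondary objectives will be analyzed with tests for repeated measures to determinate the evolution of the variables throughout study visits". The next sentence adds: "P values <0.05 will be considered as statistically significant". No objective is excepted and no specific test is named.

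Descriptive reporting is also planned. Section 7.1 says "All variables recorded will be descriptively analyzed" and "Categorical variables will be presented as frequencies and proportions", and 7.2 repeats that binary variables are given as percentages. Section 7.3 assigns stratification factors such as sex, age, radiological findings and treatment history to tests for independent measures.

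On data collection, the work plan (9.1) says of visits 2 and 3 that "adverse events should be investigated", through a question about the time since the last visit. For visit 4 it lists pain medication over the preceding month and VAS; visit 5 repeats visit 4. Sections 6.2 and 8.3 also provide, without a visit schedule, for events seen by the doctor, reported spontaneously or elicited by non-leading questions.

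**The concern.** A repeated-measures test asks whether a quantity measured several times in the same patient changes over time. That is the right question for OKS, VAS and use of rescue medication. It is not the question behind the other two secondary objectives.

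The safety objective asks how many treated patients have an adverse event, and of what kind. A comparison between visits does not estimate that. Population characteristics are fixed attributes, so there is no change to test.

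The study is a post-market follow-up with safety in its title. If the sentence is followed, the only inferential statement on safety will be a P value for change across visits. It could be read as a safety signal, or as reassurance, when it reflects how long each reporting window was and how patients were asked.

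**Working it through.** **Fit of the method to each secondary objective**

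| Objective | When recorded (9.1, 7.3) | Does a test of evolution fit? |
|---|---|---|
| Rescue medication | Visits 4 and 5, each for the preceding month | Yes |
| Adverse events | Visits 2 and 3, as events since the prior visit; other reports unscheduled; no baseline value | Computable on per-visit yes/no data, but does not give incidence |
| Population characteristics | Once | No hypothesis exists |

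**What a test across visits would show for adverse events**

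From the protocol: n = 300 (5.6); injections on day 1, week 1 and week 2 (5.5); assessments at 4 and 26 weeks (7.2). Counted from the first injection, visits 2 to 5 fall at weeks 1, 2, 4 and 26, which gives windows of 1, 1, 2 and 22 weeks.

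Assumed, because the protocol gives no event rate and names no test: a constant weekly hazard h; independent events; Cochran's Q as the test; and, for the four-window case only, adverse events counted at visits 4 and 5.

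The chance of an event in a window of w weeks is p = 1 − exp(−h·w). At h = 0.001 the expected numbers of patients with an event are:

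- 1 week: 300 × (1 − exp(−0.001)) = 0.30
- 2 weeks: 300 × (1 − exp(−0.002)) = 0.60
- 22 weeks: 300 × (1 − exp(−0.022)) = 6.5

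The risk is the same throughout, yet the last count is about 22 times the first. With k windows, window totals C, patient totals R and grand total N, Q = (k − 1)(k·ΣC² − N²)/(k·N − ΣR²), referred to chi-square on k − 1 degrees of freedom. Simulated rejection rates at 0.05:

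| Windows (weeks) | h = 0.05% per week | 0.1% | 0.25% |
|---|---|---|---|
| 1, 1, 2, 22 | about 52% | about 85% | over 99% |
| 1, 1, 4, 20 (1 month counted from the third injection) | about 39% | about 75% | about 99% |

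With only the two scheduled windows of one week each, the rates are about 0%, 1%, 3% and 5% at h = 0.1%, 0.25%, 0.5% and 1% per week. The test then keeps its level, but it only compares week 1 with week 2.

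**What an incidence estimate would show**

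Exact (Clopper-Pearson) 95% limits for x of n patients are the 2.5% point of Beta(x, n − x + 1) and the 97.5% point of Beta(x + 1, n − x). With n = 300:

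- 0/300: 0 to 1.2%
- 3/300 (1%): 0.2 to 2.9%
- 9/300 (3%): 1.4 to 5.6%

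These limits state what the planned sample can show about safety; the P value across visits does not.

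**The case against.** The strongest reply has four parts.

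1. **Incidence is already planned.** This stands. A reader might infer that the P value replaces the incidence, but 7.1 and 7.2 require frequencies, proportions and percentages. Nor is the lack of a confidence interval in the protocol a fault in itself, since that detail may sit in a statistical analysis plan that is not at hand. What remains is that the protocol does name an inferential method, and it is the wrong one for this objective.
2. **A paired test on adverse events is not invalid.** This also stands. A yes/no response at visits 2 and 3 in the same patient is paired binary data, and McNemar's or Cochran's test on it is legitimate. It is uninformative for the safety objective, not invalid.
3. **The high rejection rate needs a schedule that the protocol does not set.** Correct. The 85% requires counts at visits 4 and 5, and 9.1 schedules no adverse-event questioning there. It shows what would happen if the events collected under 6.2 and 8.3 were allotted to those visits. It is not a property of the plan as written.
4. **No analyst would run such a test on sex or age.** Probably so, and 7.3 already points elsewhere for such factors. But 7.2 makes no exception, so the two sections do not sit well together and the wording should be put right.

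**Conclusion.** The point holds in a limited form. The blanket sentence in 7.2 misapplies repeated-measures testing to two of the three secondary objectives. For population characteristics there is nothing to test. For adverse events the test does not address incidence: with the two scheduled one-week windows it is harmless but empty (rejection at most about 5% under constant risk), and with later events added it would mostly reflect unequal windows and a change in the mode of questioning. The size of that second effect (75 to 85% at 0.1% per week, depending on how the windows are counted) rests on the assumed hazard, windows and test.

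It would go too far to say that the plan will produce a false safety signal, or that adverse-event incidence will go unreported. Descriptive reporting is planned, the study calls itself descriptive, and no decision in the protocol depends on this P value. The severity is modest. It is still worth correcting, because an analysis plan that followed 7.2 would inherit the mismatch and one that departed from it would contradict the protocol.

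**What to change.** Reword one passage in 7.2:

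- Limit the repeated-measures sentence to OKS, VAS and rescue medication. Rescue medication must stay in, since it is recorded at visits 4 and 5 and suits the method.
- For adverse events, drop the P value across visits. Report the number and percentage of injected patients with at least one event, with an exact 95% confidence interval.
- For population characteristics, refer to the descriptive statistics of 7.1.

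The cost is a text change. No new data, visits or patients are needed.

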### **Study Rationale**

The current study is designed to assess the effectiveness and safety of Suplasyn® 2ml injections in a 26-week, international, multicenter, non-interventional observational study of patients recommended with one 2 ml intra-articular injection of Suplasyn® per week for three consecutive weeks with for the treatment of knee osteoarthritis. The intention is to assess the efficacy and safety of the treatment in real-life practice. Our primary target is to obtain and verify long-term outcomes from a naturalistic primary care experience.

Rationale for using viscosupplementation is to restore the protective viscoelasticity of synovial hyaluronic acid, decrease pain and improve mobility. Immediate benefit of viscosupplementation is the relief of pain while long-term benefits results are believed to include the return of joint mobility by the restoration of trans-synovial flow and the metabolic and rheological homeostasis of the joint (31). Short duration of HA within the joint does not fully explain the indisputable long-term clinical efficacy seen in practice (32).

In this case, it is appropriate to evaluate, under real-life conditions, the short-term and long-term effectiveness of triple Suplasyn® 2ml intra-articular injections and to how the extended treatment regime may impact patient satisfaction or treatment safety.

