# 5.2 Study Design

Observational Model: Case-Only; Time Perspective: Prospective study

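### A multi-part primary endpoint, tested unordered against zero change at P<0.05 with no comparator, cannot support the efficacy aim of a study that calls itself descriptive

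*Protocol*

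**What the plan says.** Section 7.2 speaks of one primary endpoint but gives it several parts. It begins "The primary efficacy endpoint is the change from baseline in the Oxford knee score" at 4 and 26 weeks and then adds the patient-rated pain "assessment (100 mm visual analogue scale/VAS) at 4 and 26 weeks". The VAS entry in section 6.2 says pain is "measured at rest (night) and during daily activities", and the work plan in 9.1 repeats both ratings. No section says which rating is the pain endpoint.

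On analysis, 7.2 says that primary and secondary objectives "will be analyzed with tests for repeated measures to determinate the evolution of the variables throughout study visits", and that "P values <0.05 will be considered as statistically significant". It gives no order among the comparisons and no rule on whether one or all must be significant.

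On design, section 5.2 reads "Observational Model: Case-Only; Time Perspective: Prospective study". Section 5.6 calls the study descriptive and says "a minimum margin to obtain statistical significance has not been settled"; its figure of 300 patients is an estimate of availability. The Study Rationale nevertheless says "The intention is to assess the efficacy and safety of the treatment in real-life practice", and 7.2 gives effectiveness as what the primary outcome assesses.

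**The concern.** Two separate problems meet in 7.2.

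The first is selection. Two scales, two time points and two VAS ratings share the name of one primary endpoint and are unordered, so whichever looks best can be reported as the primary result.

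The second is attribution, and it matters more. With no comparator, the test asks only whether the mean change differs from zero. Patients enter when they consult with a symptomatic knee (sections 4 and 5.3), so some improvement may be regression to the mean or natural course. Analgesics and NSAIDs are allowed as rescue (5.5), and their use is a secondary objective rather than part of the primary comparison. Any of these can move the mean off zero. Read as written, a significant change would be reported as efficacy.

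**Working it through.** **Sample size.** The 300 in 5.6 cannot be reproduced or refuted: the protocol gives no effect size, SD, power or dropout.

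**Number of comparisons (6.2 and 7.2).**
- Both VAS ratings: OKS × 2 times + VAS rest × 2 + VAS activity × 2 = 6.
- One VAS rating: 2 + 2 = 4.
- One omnibus repeated-measures test per scale: 2 or 3.

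**Chance of at least one P<0.05 when there is no true mean change.** This assumes two-sided tests (7.2 does not state sidedness) and that any one significant result counts as success. For k independent tests the chance is 1 − 0.95^k. For correlated tests it was simulated from a multivariate normal with a common, assumed correlation.

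| Tests | Independent | Corr. 0.3 | Corr. 0.5 | Corr. 0.7 | Corr. 0.8 |
|---|---|---|---|---|---|
| 2 | 9.75% | | | | |
| 3 | 14.3% | | | | |
| 4 | 18.5% | 17.4% | 15.7% | 13.1% | 11.4% |
| 6 | 26.5% | 24.2% | 20.7% | 16.4% | 13.9% |

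If all comparisons had to be significant, there would be no inflation.

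**Smallest observed change that is significant at n = 300.** In units of the SD of the change, this is t(0.975; 299)/√300 = 0.114. The protocol gives no SD, so these are assumed:
- VAS, SD of change 20, 25, 30 mm: 2.3, 2.8, 3.4 mm on the 100 mm line.
- OKS, SD of change 6, 8, 10 points: 0.7, 0.9, 1.1 points on the 12 to 60 scale.

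**Power of one test against a drift that treatment did not cause.** One-sample t-test on change, two-sided 0.05, noncentrality = drift × √n. At n = 300, drifts of 0.15 and 0.2 SD give noncentralities of 2.60 and 3.46.

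| Drift (SD of change) | n = 300 | n = 240 | n = 200 |
|---|---|---|---|
| 0.10 | 41% | 34% | 29% |
| 0.15 | 74% | 64% | 56% |
| 0.20 | 93% | 87% | 80% |
| 0.25 | 99% | 97% | 94% |

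The smaller sizes show the effect of missing 26-week data or a recruitment shortfall.

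One illustration of how such a drift could arise: let the baseline mean lie d SDs above the patients' usual level, with retest correlation r. Regression to the mean is then (1 − r) × d × SD, and the SD of change is SD × √(2(1 − r)). With SD 20 mm and r = 0.5, the SD of change is 20 mm. Then d = 0.3 gives 3 mm (0.15 SD) and d = 0.5 gives 5 mm (0.25 SD). All these inputs are assumed.

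**Would alpha adjustment be enough?** Bonferroni gives 0.05/4 = 0.0125 or 0.05/6 = 0.0083 per test. At n = 300 and a drift of 0.2 SD, power per test falls from 93% to 83% or 79%. Adjustment deals with selection among tests but leaves attribution untouched.

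**The case against.** The main objective in 3.1 is to assess changes in clinical outcome, and a within-patient comparison does that. The protocol says openly that it is observational, case-only and descriptive. It claims no superiority and no power, and sets no success criterion. Ordering of endpoints and multiplicity methods are commonly left to a statistical analysis plan, which may exist. Six tests is an upper bound, and the error rates in the table presume that any one significant result is enough. Eligibility sets no minimum pain or OKS score and sampling is consecutive, so the protocol gives no basis for sizing regression to the mean.

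Much of this stands. The absence of a named multiplicity method is not in itself the defect, and the drift figures remain conditional. What the objection does not remove is what the protocol itself fixes: a singular primary endpoint with several parts, a significance threshold, and an efficacy aim beside a descriptive, uncontrolled design. An analysis plan could order the tests, but it could not supply a comparator.

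A reader might also infer that six tests make a significant result nearly certain. The documents do not support this: with no true change the chance is at most about 26%. Near-certainty needs a real mean shift. At n = 300 and a drift of 0.15 SD, at least one of six is significant in 93% to 99% of studies (correlation 0.7 to 0.3), but the protocol states no drift. With a shift of 0.25 SD, a single test already has 99% power, so the number of tests hardly matters.

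**Conclusion.** The point holds in two parts, which should be kept apart.

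- **Selection among comparisons.** Section 7.2 leaves 4 to 6 unordered comparisons under one primary endpoint, or 2 to 3 if omnibus. The chance of a false positive is about 10% to 26% under independence and an any-one rule. It is lower with correlation: about 21% for six tests at 0.5.
- **Attribution.** This does not depend on the count. Rejecting zero change cannot show efficacy without a control. At 300 patients the test detects very small shifts: 0.11 SD observed is significant, and a drift of 0.15 to 0.2 SD, if present, gives 74% to 93% power per test. The SDs, drifts and correlations are assumptions; the protocol gives none.

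It would go too far to say that the plan guarantees a positive result, or that the design fails its stated main objective. The study can describe change after treatment. It cannot attribute that change to Suplasyn, and the efficacy wording suggests that it can. The point should be acted on; it does not stand in the way of the study.

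**What to change.** In 7.2, name one primary scale and one time point. OKS total at 26 weeks would be one choice, consistent with the long-term target in the Study Rationale. Name one of the two VAS ratings as the pain endpoint. State that the other comparisons are tested in a given order or are descriptive.

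Make the mean change with its 95% CI the main result. At 300 patients with complete data, the half-width would be about 2.3 to 3.4 mm on the VAS for an assumed SD of change of 20 to 30 mm. A clinically important change may be cited as an aid to interpretation. It should not serve as a hurdle that proves efficacy, because clearing it would still not permit attribution.

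Reconcile the Study Rationale, 5.6 and 7.2 so that all three describe the conclusion as within-patient change after treatment, not attributable to Suplasyn without a control.

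The cost is wording only: no new visits, data or patients. The downside for the sponsor is a more modest claim.
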